This will be a prospective randomized study comparing outcomes of pediatric patients who are treated with NAVA versus BiPAP respiratory support following cardiac surgery. Subjects will include pediatric CVCC patients who undergo cardiac surgery from October 2016 through October 2017 and who are up to 12 months of age. As patients recover from cardiac surgery, they are extubated and may require further respiratory support. If so, they receive CPAP support and then are transitioned to one of two modalities: either NAVA or BiPAP support. Both modalities are routinely used in the Children's CVCC, and the investigators will compare if one modality produces more favorable outcomes than the other. Following CPAP, enrolled subjects will be randomized to receive either NAVA or BiPAP, and their remaining clinical course will follow standard care. Specific measures following initiation of respiratory support will be collected, in addition to characteristics of the operative procedure and patient diagnoses. The study aims to compare duration of respiratory support, sedation requirements, and hospital length of stay between the two modalities.

Time Frame/Duration

This study will be conducted over an 18-month period to allow for subject enrollment, data collection, analysis, and manuscript preparation.

Activity		Month																
	1	2	3	4	5	6	7	8	9	10	11	12	13	14	15	16	17	18
IRB approval																		
Recruitment/enrollment																		
Data collection/ chart abstraction																		
Analysis																		

Manuscript preparation									

Analysis

Sample Size

We will enroll all consecutive patients who are eligible for inclusion in the 12-month enrollment period and consent to participation, up to 40 patients. An interim analysis will be performed after 20 patients are enrolled to assess means and variance of the primary outcomes, and reassess sample size.

Analytic Approach

Exploratory analysis methods will be used to describe the enrolled patient population, including mean and standard deviation for continuous variables such as length of hospital stay, sedation needs, and intubation as well as frequency and percentage for categorical variables such as STAT score and type of non-invasive PPV.

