For the continuous outcomes of interest (duration of non-invasive respiratory support, length of hospital stay and sedation needs), either a two-sample t-test or non-parametric Mann-Whitney U test will be used to compare those patients who received NAVA or BiPAP. For categorical variables, either a chi-square test or Fischer's exact test will be used to compare the two groups. Additional regression analysis will adjust for procedure severity.

Statistical significance will be defined as p < 0.05.

5. Subjects

Subjects

We plan to enroll 40 subjects 0 to 12 months of age at time of cardiac surgery over a 1 year period.

Identification of Subjects, Recruitment, and Enrollment

Potential subjects will be identified by monitoring the cardiovascular surgery schedule, and eligibility will be confirmed by the provider. Patients who meet all of the inclusion criteria and none of the exclusion criteria will be approached for consent by study staff. Not all cardiac patients receive NIV support postoperatively, and the decision to provide NIV support is not made by the provider until after the surgery. This will happen either while the patient is intubated, or immediately following extubation. Written informed consent will be sought from parents/guardians. Assent will not be sought in this young patient population. Patients who enroll will be assigned a unique study ID. A log of enrolled subjects will be maintained, and will only be accessible by approved study staff. The target enrollment is 40 patients.

Inclusion Criteria:

- Postoperative cardiac surgery patients admitted to the CVCC
- Recommended for NIV respiratory support following extubation, per provider discretion
- 0-12 months of age

Exclusion Criteria:

- Tracheostomy in place at time of cardiac surgery
- Chronic lung disease
- Pre-operative non-invasive respiratory support

6. Study Procedures

Data Requirements

The data elements will be collected by the research study staff from the subject's electronic medical record. These will include:

- Demographic Data (name, date of birth, age at admission, admission date/time, cardiac diagnosis, comorbidities)
- Operative Data (surgeon, date of procedure, intubation/extubation date/time, date/time returned to CVCC)
- Adverse Event Information (description of event and day post-cardiac surgery that the event(s) took place)

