- Medication Data (daily amounts of dexmedetomidine, fentanyl (total fentanyl and boluses of pca fentanyl), midazolam, morphine, lorazepam for up to 14 days postoperatively, date/time patient is on/off the above medications)
- Post-Operative Respiratory Support Data (type of non-invasive respiratory support used, date/time on off CPAP, date/time on/off biPAP/NAVA)
- Pain and Sedation Score Data (daily FLACC/SBS scores for up to 14 days postoperatively)
- Discharge Data (discharge date/time, length of hospital stay, survival at discharge, date/time of death [if applicable], cause of death [if applicable])

Visit Schedule

Eligible patients will be recruited during their admission to the CVCC. Upon enrollment, patients will be randomized to receive either NAVA or BiPAP. What respiratory modality the patient will receive will be determined by drawing a slip of paper from a sealed envelope. Following randomization and provision of respiratory support, patient care will be per standard care. Patient data will be only collected for the reference admission period. There will be no follow-up visits or activities required of the patient for this study following enrollment.

Drug/Device, Handling, Storage (If Applicable)

All devices in this study are currently used and stored in the CVCC. They will continue to be used as per CVCC SOPs.

7. Risks/Benefits

Potential Risks

Subjects will be randomized to respiratory support treatments that are already incorporated into standard care. The potential risks from these treatments are no more than those experienced as part of standard care. There is a risk associated with privacy of personal health information, and there is a risk of breach of confidentiality.

Methods to Minimize Risks

Both NAVA and BiPAP are non-invasive modalities that are safely used in standard care. Providers will follow SOPs for the use of NAVA and BiPAP support to minimize risks. If complications occur, standard care will be provided and patients will be treated accordingly. Electronic data will be stored on secure password-protected computers in limited access files, in a locked office suite. Any paper records will be stored in locked cabinets that only approved study staff have access to. This is a single-site study, and no identifiable patient data will be shared outside of the IRB-approved study staff. Any results from the study will be published in aggregate form, preventing any individual patient's data from being identified.

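### Daily sedation data stop 14 days after surgery while NAVA or BiPAP starts on an unrestricted later day, so Aim 2 has unequal post-device windows and no stated time origin

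*Combined protocol and SAP*

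**What the plan says.** Section 6, Data Requirements, lists the daily amounts of five sedative and analgesic drugs and limits them by time since surgery: "midazolam, morphine, lorazepam for up to 14 days postoperatively, date/time patient is on/off the above medications". Pain and sedation scores carry the same limit: "Pain and Sedation Score Data (daily FLACC/SBS scores for up to 14 days postoperatively". Device on/off times and discharge time are listed with no such limit. The source is the chart ("The data elements will be collected by the research study staff from the subject's electronic medical record"), and the Visit Schedule sets the outer boundary: "Patient data will be only collected for the reference admission period".

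Section 4, Study Design, places the device after surgery, extubation and CPAP: "they receive CPAP support and then are transitioned to one of two modalities: either NAVA or BiPAP support". It gives no latest postoperative day for that step. It also describes the intended data by a different origin: "Specific measures following initiation of respiratory support will be collected".

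The time of randomisation is given in two ways. Study Design says "Following CPAP, enrolled subjects will be randomized to receive either NAVA or BiPAP"; the Visit Schedule says "Upon enrollment, patients will be randomized to receive either NAVA or BiPAP".

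The sedation outcome appears as duration of sedation in the background, as sedation requirements in Aim 2, and as sedation needs under Analytic Approach. None of these has a start point or a length. The planned test is a t-test or Mann-Whitney U test, with no rule for records cut at day 14. The regression adjusts only for procedure severity. Appendices 3 and 4 (study schema, data collection forms) appear by title only in the public text, so they could not be checked.

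**The concern.** The collection window is anchored on surgery, but the comparison concerns what happens after the device starts. Two separate problems follow.

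1. **Cap.** An infant who starts late has a short post-device record. If sedation or scoring continues past day 14, the later amounts and scores are not collected. If one arm is sedated longer, that arm is cut more often, so a real difference looks smaller.
2. **Origin.** Because the daily window begins at surgery, an analyst could count sedation from surgery. Time before the device, which the device cannot affect, would then be added to the outcome. It is balanced between arms in expectation but adds noise, and with 40 patients it can be unbalanced by chance. The choice of origin matters for length of stay too; the day-14 limit does not affect stay.

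At stake is the ability of Aim 2 to detect a difference in a small trial.

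**Working it through.** **Inputs.** From the documents: limit at day 14 after surgery, 40 patients in total, significance at p < 0.05. The documents give no start days, sedation durations, effect size, SD, power or allocation ratio, so there is no figure of the plan's own to reproduce. Everything else below is assumed, including 20 per arm and a two-sided test.

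**Step 1: window.** With device start on postoperative day S, the longest observable post-device record is W = 14 − S: 11, 7 and 4 days for S = 3, 7 and 10. An infant sedated for D days after device start loses max(0, D − W) days. A 7-day course loses 0, 0 and 3 days; a 10-day course loses 0, 3 and 6.

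**Step 2: cap alone.** Let post-device sedation be exponential with mean m. The share still sedated after day 14 is exp(−W/m), and the observed mean is m × [1 − exp(−W/m)]. For means of 3 days (BiPAP) and 2 days (NAVA), the true difference is 1 day:

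- S = 3: 2.923 − 1.992 = 0.931, so 93% is seen
- S = 7: 2.709 − 1.940 = 0.769, so 77% is seen
- S = 10: 2.209 − 1.729 = 0.480, so 48% is seen
- fixed 14 days from device start: 97% is seen

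With means of 2 and 1.33 days the shares are 99%, 92% and 69%, against 99.7%. With 6 and 4 days they are 65%, 41% and 20%, against 77%.

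**Step 3: power.** Simulation with the Mann-Whitney test. Start day S is lognormal (median 2, 4 or 6; log SD 0.6). Post-device sedated days D are lognormal (log SD 0.8; BiPAP median 3 or 6). The NAVA/BiPAP ratio is exp(−0.909 × 0.8) = 0.483, chosen to give 80% power on the log scale. S and D are independent. Sedated days stand in for the capped amounts and scores. Infants who start after day 14 (about 8% at median start day 6) have no observed window and are set to missing. Runs agree to within about 2 points.

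| Outcome | BiPAP median 3 days; start median 2 / 4 / 6 | BiPAP median 6 days; start median 2 / 4 / 6 |
|---|---|---|
| Post-device days, cut at day 14 | 78 / 74 / 67% | 77 / 71 / 59% |
| Post-device days, fixed 14-day window | 77-78% | 77-78% |
| Days from surgery, no cap | 55 / 36 / 25% | 69 / 56 / 45% |

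Adding the cap to the last row changes it by 0 to about 4 points, so nearly all of that loss comes from the origin. The expected number of the 40 infants sedated past day 14 is 1.2, 3.4 and 7.7 (median 3) or 5.2, 8.9 and 13.9 (median 6). With no true effect, rejection rates were 4.7% to 5.1%.

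**Step 4: covariate.** Adjusting a log-scale comparison for pre-device sedated time gives about 85% power against 79-80% unadjusted if its correlation with the outcome is 0.4. If the correlation is 0 it gives 78-79%, a cost of about 1 point.

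**The case against.** The strongest case against has four parts.

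- **The cap may not touch the outcome.** The background names duration of sedation, and the drug on/off times follow the 14-day phrase as a separate item, so they may be uncapped. This stands as far as it goes: a duration outcome may be recoverable past day 14. Daily amounts and scores would not be, and Aim 2 speaks of requirements. A reader might infer that all sedation information after day 14 is lost; the documents do not support that.
- **The large power losses are not due to the cap.** This is correct. A reader might credit the fall to about 25% to the day-14 limit, but the same loss occurs with no limit at all.
- **The cap loss depends on how late starters are scored.** This is also correct. Scoring infants who start after day 14 as zero would give 56% and 48% at median start day 6. Setting them to missing gives about 67% and 59%, the figures used here.
- **Materiality is not shown.** Every clinical input is assumed, the simulation uses sedated days and not amounts or scores, and at median start day 2 the cap costs essentially nothing. Nothing in the documents indicates late starts, and later days could still be taken from the chart. This limits how strongly the point can be put. It does not remove it, because the written rule gives infants unequal post-device windows and a better rule costs almost nothing.

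**Conclusion.** The point holds as two separate issues, and the plan should be changed, though neither undermines the trial.

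- **Cap:** followed as written, the plan cuts post-device amounts and scores for infants still sedated or scored after day 14, and so can shrink a real difference. In the assumed model the loss ranges from nothing (median start day 2) to about 10 points (BiPAP median 3 days) or nearly 20 points (6 days) at median start day 6. The true size is unknown and may be nil.
- **Origin:** no start point is stated for sedation or stay. Counting sedation from surgery would cost far more power in the same model, about 10 to 50 points, with or without the cap.

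A reader might infer that the cap favours one arm or produces false positives. It does not: the limit is the same in both arms, and error rates with no effect stayed near 5%. Nor does it affect Aim 1, since device on/off times carry no stated limit.

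**What to change.** 1. Keep daily amounts and scores from surgery as baseline. Run the collection window for a fixed time within the admission, for example 14 days, from device start, or from randomisation once Study Design and Visit Schedule are reconciled on when that occurs.
2. Analyse sedation and length of stay from that same point, and state which calendar day counts as day 1. Stay from device start follows from times already listed. Keep total hospital stay as a description.
3. Define the sedation outcome, and say whether the drug on/off times are collected past day 14.
4. Add pre-device sedation, which is already collected, as a covariate in the planned regression. If randomisation comes before device start, use sedation up to randomisation only.

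The cost is some wording, a few more days of chart abstraction for late starters, and about 1 power point if the covariate proves unrelated to the outcome. No extra visits or patients are needed.

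### Sedative amounts are daily totals counted from surgery, allocation comes later, and the plan does not exclude pre-allocation sedation from Aim 2 or use it as a covariate

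*Combined protocol and SAP*

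**What the plan says.** Section 6, Data Requirements, sets the unit and the clock for sedative amounts. The unit is the day: "Medication Data (daily amounts of dexmedetomidine, fentanyl (total fentanyl and boluses of pca fentanyl". The list continues "midazolam, morphine, lorazepam for up to 14 days postoperatively, date/time patient is on/off the above medications", so the clock starts at surgery. The same section collects "intubation/extubation date/time" and "date/time on off CPAP, date/time on/off biPAP/NAVA". A date and time of randomisation is not among the listed fields.

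Section 4, Study Design, places allocation later: "Following CPAP, enrolled subjects will be randomized to receive either NAVA or BiPAP". Section 6, Visit Schedule, instead has patients randomised when they enrol.

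The Aim 2 variable has no stated summary measure, start or end. Aim 2 speaks of sedation requirements, the end of the background speaks of duration of sedation, and the Analytic Approach lists "length of hospital stay and sedation needs" among the continuous outcomes. That section plans a t-test or Mann-Whitney test, plus a regression that adjusts for procedure severity only.

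**The concern.** Aim 2 asks whether the device changes how much sedation a child needs. Only drug given after allocation can answer that. The one window stated for amounts opens at surgery, so it also holds drug given during intubation and initial CPAP. Comparing totals over that window adds a component with the same expected value in both arms. It shrinks the relative difference and adds variance, and with so few patients a chance difference in pre-allocation sedation could be read as a device effect.

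Two further points follow. A daily total on the day NAVA or BiPAP starts mixes drug given before and after the start. And the amount given just before allocation, plausibly a good predictor of the amount needed next, is collected but has no role in the analysis.

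**Working it through.** **No figure to reproduce.** The target of 40 comes without an effect size, SD or power, so the check has two parts: what the listed fields allow, and what including pre-allocation drug would cost.

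**Part 1. What can be separated.**
- Whole days before device start: yes, from the device on-times.
- Duration of sedation from device start: yes, from the drug on/off times and device on-times.
- Amount on the switch day: not exactly. Drug on/off times help only if a drug starts or stops near the switch, or if a constant rate is assumed, and they do not place boluses.
- Weight of that day: 1/3 = 33%, 1/7 = 14% or 1/14 = 7% of the days from device start, if that period lasts 3, 7 or 14 days (assumed lengths).

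**Part 2. Cost of comparing totals.** From the documents: at most 40 patients and p < 0.05. Assumed: 1:1 allocation (20 per arm), a two-sided Mann-Whitney test, lognormal amounts with CV 0.7 in each phase, a true 40% reduction after the device, and independent phases.

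Let s be the share of the comparator arm's total that precedes allocation. Set the post-allocation mean to 1, so the pre-allocation mean is s/(1 − s).

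Apparent reduction in the total = 40% × (1 − s). Power is by simulation; with 6,000 trials per scenario the standard error is at most √(0.25/6000) = 0.6 percentage points.

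| s | Apparent reduction | Power |
|---|---|---|
| 0 (post-allocation only) | 40% | about 68% |
| 20% | 32% | about 60% |
| 50% | 20% | about 31% |
| 70% | 12% | about 14% |
| 80% | 8% | about 8% |

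**Sensitivity.**
- Gamma amounts with the same CV: 53–56% for post-allocation drug, falling to 25–27%, 11–12% and 8% at s = 50%, 70% and 80%.
- Correlation of 0.5 between phases (lognormal): the total gives about 22–24%, 12% and 7–8% at the same shares. Post-allocation drug adjusted for the pre-allocation amount on the log scale gives about 82%.
- Normal model: power = Φ(d / (SD × √(2/20)) − 1.96). With d = 0.886 and SD = 1, this is Φ(2.80 − 1.96) = 80%. Adding an uncorrelated pre-allocation amount with SD r gives total SD √(1 + r²). For r = 1, power is Φ(2.80/1.414 − 1.96) = 51%. For r = 0.5, 1.5 and 2 it is 71%, 34% and 24%. With correlation 0.5 the four values (r = 0.5, 1, 1.5, 2) are 56%, 37%, 25% and 18%.

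The size depends on the assumptions; the direction is the same in every scenario.

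**The case against.** A reader might infer that Aim 2 does include sedation given while intubated. The documents do not say so. Data Requirements list what is abstracted, not what is analysed, and Study Design says "Specific measures following initiation of respiratory support will be collected", which points to a later start. That sentence does not settle the matter, because CPAP is also respiratory support and comes before allocation. What stands is that the window is undefined and pre-allocation drug is not excluded.

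A reader might also infer that the data cannot be separated at all. They largely can: earlier whole days can be dropped, and Aim 2 read as duration of sedation avoids the splitting problem. Nor need the switch-day total contain intubated-phase drug; if extubation was on an earlier day, it mixes only CPAP-phase with device-phase drug. The data collection forms in Appendix 4 are not shown, so finer detail there cannot be ruled out. Still, the plan does not say that earlier days will be dropped, and the switch day is the first day of device exposure.

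A third stronger reading is bias. If allocation is properly random, pre-allocation drug has the same expected amount in both arms, so the harm is noise and chance imbalance. Leaving out a baseline covariate is a loss of precision, not an error.

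Finally, the shares from 20% to 80% are assumed. The documents give no doses, intubation times or CPAP durations, and the losses apply only if whole-record totals are compared.

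**Conclusion.** The point holds in a limited form. Amounts are daily and counted from surgery, allocation comes after extubation and CPAP, and no sentence keeps pre-allocation drug out of Aim 2. The switch-day amount cannot be split from the listed fields, and the pre-allocation amount is unused. If totals over the whole record were compared, power could fall only modestly (68% to about 60% at a 20% share) or almost completely (about 8% at 80%), on the assumed values above. The documents do not support a claim that Aim 2 is biased, or that its analysis is already fixed to include pre-allocation sedation. It is worth correcting because the trial is small and the correction is cheap.

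**What to change.** 1. Reconcile the two statements on when randomisation happens (at enrolment in Visit Schedule, after CPAP in Study Design), and add its date and time to the collected data. Otherwise counting from randomisation could still take in intubated-phase drug.
2. Define the Aim 2 amount as drug given after the post-CPAP allocation. Abstract each drug in 24-hour blocks from that time, and state how many blocks are counted. If the record lacks timed doses, start at the first full calendar day after allocation.
3. Adjust the Aim 2 comparison for the sedative amount in the 24 hours before allocation (or the last full day before it), alongside procedure severity.

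The cost is a revised abstraction form and a sentence or two in the analysis section; the source is still the electronic medical record. The downside is slightly more abstraction work or, under the whole-day option, loss of the switch day. Patient care is not affected.

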NAVA has recently been adopted for non-invasive respiratory support in the Children's Hospitals and Clinics of Minnesota CVICU, the cardiovascular care center (CVCC). Close to 10% of CVCC post-operative patients receive a form of bi-level NIV support, either NAVA or BiPAP. The frequency of NIV use in neonates (0 to 28 days of age) can be 30% or higher. We propose a randomized study to compare clinical outcomes following use of NAVA versus BiPAP in CVCC patients following cardiac surgery. Specifically, we will compare duration of NIV, duration of sedation, and hospital length of stay.

Research Question

Is the use of synchronized biphasic support with NAVA associated with shorter duration of noninvasive respiratory support, less sedation requirements, and reduced hospital length of stay compared to conventional BiPAP?

4. Study Design and Methodology

Aim 1: To assess whether the use of neurally adjusted ventilator assist (NAVA) is associated with a shorter duration of non-invasive respiratory support compared to conventional BiPAP. **Aim 2:** To assess whether the use of neurally adjusted ventilator assist (NAVA) is associated with less sedation requirements compared to conventional BiPAP.

Aim 3: To assess whether the use of neurally adjusted ventilatory assist is associated with reduced hospital length of stay compared to conventional BiPAP.

Hypothesis: Synchronized biphasic support with NAVA will be associated with shorter duration of non-invasive respiratory support, less sedation requirements, and reduced hospital length of stay.

Overview/Scope

Study Design

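### Aim 3 gives hospital length of stay no start point; counted from admission, it includes pre-randomisation days whose variation between infants costs precision

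*Combined protocol and SAP*

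**What the plan says.** - **Outcome.** Section 4, Aim 3: "To assess whether the use of neurally adjusted ventilatory assist is associated with reduced hospital length of stay compared to conventional BiPAP". Under Analytic Approach, length of stay is one of three continuous outcomes compared by a t-test or Mann-Whitney test. A further regression adjusts for procedure severity only.
- **Data.** Section 6, Data Requirements, lists "age at admission, admission date/time, cardiac diagnosis, comorbidities" and, at discharge, "discharge date/time, length of hospital stay, survival at discharge". It gives no formula for the stay. It also lists "date/time on off CPAP, date/time on/off biPAP/NAVA", but no randomisation date or time. Visit Schedule limits data to the reference admission.
- **When treatment is decided.** Section 5, on identification and recruitment: "the decision to provide NIV support is not made by the provider until after the surgery".
- **When randomisation occurs.** Section 4, Study Design: "Following CPAP, enrolled subjects will be randomized to receive either NAVA or BiPAP, and their remaining clinical course will follow standard care". Section 6, Visit Schedule: "Upon enrollment, patients will be randomized to receive either NAVA or BiPAP".
- **Sample size.** Up to 40 infants aged 0 to 12 months, with no effect size, SD or power given.

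**The concern.** An outcome meant to show the effect of a randomised device is best counted from a point at or after allocation. Here the natural reading starts the clock at hospital admission. The need for NIV is decided only after surgery, so any preoperative days precede randomisation whichever randomisation statement is followed. If randomisation follows CPAP, ventilated and CPAP days precede it too. None of that time can respond to NAVA or BiPAP.

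The amount of such time can be expected to differ between infants. The trial takes newborns and infants up to 12 months, and it sets no limit on preoperative stay or on ventilation before extubation. With at most 40 infants, that variation could take a material share of whatever power Aim 3 has. A stated start point would also prevent the choice of clock from being made after the data are seen.

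**Working it through.** **1. The plan's own figure.** The target of 40 cannot be reproduced, because no difference, SD or power is stated. A reference case is needed. Assumptions: 1:1 allocation (20 per arm), two-sided 5% level, 80% power on post-randomisation stay. The standardised difference detectable is then

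d = (1.960 + 0.842) × √(2/20) = 0.886 post-randomisation SDs (0.909 with the noncentral t).

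**2. Effect of adding pre-randomisation days.** Whole stay = pre + post. Under randomisation the expected difference in mean days between arms is unchanged. Let r = SD(pre)/SD(post) and ρ their correlation. The SD is multiplied by

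f = √(1 + r² + 2ρr),

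and power ≈ Φ(0.886 × √(20/2) / f − 1.960) = Φ(2.802/f − 1.960). The number per arm that restores 80% power is 20 × f², rounded up. Both r and ρ are assumptions.

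| ρ | r | f | Power | Per arm for 80% |
|---|---|---|---|---|
| any | 0 | 1.000 | 80.0% | 20 |
| 0 | 0.25 | 1.031 | 77.6% | 22 |
| 0 | 0.5 | 1.118 | 70.7% | 25 |
| 0 | 1 | 1.414 | 50.8% | 40 |
| 0.3 | 0.25 | 1.101 | 72.1% | 25 |
| 0.3 | 0.5 | 1.245 | 61.4% | 31 |
| 0.3 | 1 | 1.612 | 41.2% | 52 |
| 0.5 | 0.25 | 1.146 | 68.6% | 27 |
| 0.5 | 0.5 | 1.323 | 56.3% | 35 |
| 0.5 | 1 | 1.732 | 36.6% | 60 |

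**3. Where there is no loss.** The row r = 0 is a constant offset. It shifts both arms equally, leaves the SD and the ranks alone, and costs nothing under either test. The penalty also vanishes at ρ = −r/2 and reverses below that. With ρ = −0.3, power is 83.5% at r = 0.25, 82.0% at r = 0.5 and 65.8% at r = 1.

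**4. Rank-test check on skewed data.** Simulation with 4,000 trials per setting and 20 per arm. Assumptions: post-randomisation stay log-normal (median 12 days, log-SD 0.7), cut by 40% with NAVA; pre-randomisation time log-normal (log-SD 0.8). Mann-Whitney power on post-randomisation stay is about 58–60%. On whole-admission stay:

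| Correlation (log scale) | Median pre 3 days | 6 days | 10 days |
|---|---|---|---|
| −0.3 | 56% | 45% | 34% |
| 0 | 48% | 37% | 27% |
| 0.4 | 43% | 30% | 21% |

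With a median of 1 or 2 days and no correlation, power is 56% and 53%. With constant offsets of 3, 6 or 10 days it is unchanged. With no treatment effect, the rejection rate on whole-admission stay is 4–5%.

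**5. Relative effect.** If 20% of the stay precedes randomisation, a 25% cut in later stay appears as 25 × 0.8 = 20% of the whole. If 50% precedes it, the cut appears as 12.5%. This affects how the result reads; the absolute difference in days is the same.

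**6. Adjustment.** In a linear regression of whole stay on arm and pre-randomisation days, the arm coefficient is identical to that from regressing post-randomisation stay on the same terms. The residual SD is SD(post) × √(1 − ρ²), so adjustment removes the penalty. The plan does not include this covariate.

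**The case against.** Several points on the other side stand.

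- **Admission to discharge is inferred.** The documents never define the stay that way. The defect is an unstated start point. The data collection forms and study schema (Appendices 3 and 4) are not visible here and may contain a definition or a randomisation time field.
- **Fixed time does not dilute the test.** A reader might infer that any pre-randomisation time weakens the comparison. Only its variation between infants does.
- **Chance imbalance is not bias.** A reader might also infer that longer preoperative stays in one arm could pass for a device effect more often than the test allows. The 5% level already covers such imbalance; what is lost is precision.
- **Not all of the time is certainly pre-randomisation.** If randomisation is at enrolment, CPAP and some ventilated time may follow it. Only preoperative days precede it on both statements.
- **The size is wholly assumed.** With a 20% reduction instead of 40%, simulated power is only about 16–17% even from randomisation, and 14%, 11% and 9% on whole-admission stay at 3, 6 and 10 days with no correlation. Neither clock is then adequate.
- **Total stay is a legitimate resource outcome**, and a stay from device start can be computed from times already collected. The planned severity adjustment may absorb some of the variation.

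These limit the claim but do not remove it. No later clock is planned, and none of the visible text excludes time that the device cannot affect.

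**Conclusion.** The point holds as one of definition and precision. Aim 3 has no stated start point, and on its ordinary reading it counts time settled before allocation, with no adjustment for that time. From a reference of 80% power at 20 per arm, the loss ranges from about 2 percentage points (r = 0.25, ρ = 0) to about 43 (r = 1, ρ = 0.5). It can be nil or reversed if pre-randomisation time is nearly constant or negatively correlated with later stay. These figures rest on assumed SD ratios, correlations, 1:1 allocation and a two-sided test, because the documents contain no stay data.

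The documents do not support a claim of systematic bias or of excess false positives. The change is worth making because it improves precision under most plausible assumptions at almost no cost. It would not by itself make Aim 3 adequately powered.

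**What to change.** 1. State under Analytic Approach that the Aim 3 outcome is days from randomisation to hospital discharge.
2. Record the randomisation date and time, if the data form does not already do so. Randomisation is a safer start than device start, because it is defined for every randomised infant.
3. Reconcile Study Design (after CPAP) with Visit Schedule (at enrolment), so that the clock start is unambiguous.
4. Report admission-to-discharge stay descriptively, and show days from admission to randomisation by arm as a baseline characteristic.
5. If whole-admission stay is kept as the tested outcome, prespecify days from admission to randomisation as a covariate.

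The cost is a sentence or two of text and at most one added time field, with no extra patients or procedures. The drawback is that the tested figure is less directly comparable with published total stays; the descriptive report covers that need.
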